### 4.3 Risk-benefit assessment

There is no monitored experience in children/adolescents available for the BoNT-A preparation under investigation. NT 201 was subject to extensive toxicological and safety pharmacological testing in non-clinical as well as clinical studies, which showed that NT 201 is well tolerated and has an acceptable safety profile (see current IB [[Merz Pharmaceuticals \(GmbH\) - IB](#)]). In a juvenile toxicity study in rats, decreased mating rates and atrophy of the testicular germinal epithelium with subsequent hypospermia without functional consequences were observed at 30 Lethal Dose 50 (LD50) Units [LD50U]/kg. However, no indications of frank systemic toxicity other than growth retardation were seen at 10 LD50U/kg and below. The clinical relevance of the findings from this animal study with these extremely high doses and reinjection already at

maximal paralysis is unknown. In a clinical setting, subjects are only re-injected upon recovery of the muscle function, usually 3 to 6 months after injection of BoNT-A. In this study investigators who are informed on preclinical safety data of NT 201 will judge the clinical need for an injection in doses of up to a maximum of 20 U/kg BW NT 201 at least 12 weeks after the last injection treatment. Two clinical studies with NT 201 in adult subjects with UL muscle spasticity after stroke and other etiologies with a maximum dose of 400 U NT 201, respectively, showed good efficacy and no safety issues [Barnes 2010, Kanovsky 2011].

In general, BoNT-A is well tolerated in children/adolescents [Naumann and Jankovic 2004, Lukban 2009, Heinen 2010]. Common undesirable effects after BoNT-A injection include local, generalized, or procedural AEs. Local AEs are usually mild and self-limiting. The most commonly reported local AEs after BoNT treatment in children/adolescents are potential and expectable consequences of overshooting muscle relaxation such as excessive localized weakness [Love 2010]. Systemic AEs related to BoNT-A include nausea, fatigue, bladder incontinence, flu-like symptoms, and rash [Naumann 2006, Howell 2007]. Procedural AEs include complications due to local anesthesia or analgosedation before injection.

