## 7.1 Inclusion criteria

Only subjects meeting all of the following inclusion criteria will be considered for study enrollment:

Inclusion Criteria	Rationale	Screening (V1)	Baseline (V2)
1. Written informed consent obtained from the parent(s)  and assent by the subject (if applicable).	Administrative	X	
2. Understanding of study procedures and willingness to abide to all procedures during the course of the study by the subject (if applicable) and parent(s).	Administrative	X	

---

 The term parent(s) is used for any legally acceptable representative including guardian(s) in this study protocol as defined in the ICH guideline E6 (R1) as individual or juridical or other body authorized under applicable law to consent, on behalf of a prospective subject, to the subject's participation in the clinical trial.

Inclusion Criteria	Rationale	Screening (V1)	Baseline (V2)
3. Female or male subject 2 to 17 years of age (inclusive).	Administrative	X	
4. Uni- or bilateral CP with clinical need for injections with NT 201 for the treatment of UL spasticity at least unilaterally.	Efficacy	X	X
5. Ashworth Scale [AS] score in the main clinical target patterns in this study			
- Flexed elbow: AS score $\geq 2$ in elbow flexors (at least unilaterally)	Efficacy	X	X
and/or			
- Flexed Wrist: AS score $\geq 2$ in wrist flexors (at least unilaterally).			
6. Clinical need according to the judgment of the investigator in one out of five treatment combinations (A-E, as shown below). AS score must be $\geq 2$ for each target pattern chosen for injection at the Baseline Injection Visit V2.	Efficacy	X	X

---

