## 8 TREATMENTS

### 8.1 Investigational product(s)

#### 8.1.1 Description of investigational product(s)

In the double-blind MP, subjects will be randomly allocated to receive active treatment in one of three parallel dose groups (high, mid, and low).

In the open-label OLEX, all subjects will receive active treatment in the same dose group.

Active treatment:	NT 201, 100 units, powder for solution for injection
International non-proprietary name of active ingredient:	An international non-proprietary name for the drug substance has not been assigned. The assigned USAN for the active ingredient is incobotulinumtoxinA.
Excipients:	Sucrose, human serum albumin.

The IP will be supplied in a clear glass vial. Each vial of NT 201 contains an amount of sterile lyophilized solid material with biological activity of 100 mouse LD50U (calculated median lethal intraperitoneal dose), which corresponds to approximately 600 pg of neurotoxin. The excipients of the final formulation of NT 101 (that is the active neurotoxin molecule in the preparation of NT 201) are sucrose for stabilization and human serum albumin to prevent adsorption of the neurotoxin on container, syringe, and needle. NT 201 contains no hemagglutinins.

In MP only, PBO will be used for preparation of the injection solution for the mid and low dose group. PBO vials with lyophilisate have identical appearance and solution properties to NT 201 vials. The PBO vials contain human serum albumin and sucrose but do not contain NT 101.

PBO for IP preparation for mid and low dose group:	PBO vial containing excipients of NT 201, powder for solution for injection
Excipients:	Sucrose, human serum albumin.

The IP might be supplied in more than one shipment at different time points of the study.

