Depending on which body side(s) and limb(s) are affected by UL spasticity, uni- or bilateral UL will be administered in five treatment combinations (A-E) at Baseline Injection Visit V2 (see for details see [Table 6](#) to [Table 13](#)). It will not be allowed to change the treatment combination chosen at V2 or to change the body side of treatment in unilaterally treated subjects.

In subjects with additional treatment of LL(s) in treatment combinations B. – E. it will be allowed to change the LL patterns chosen at V2 in further treatment cycles. Regulations for doses per muscle, number of injection sites of [Table 15](#) and for total dose to the LL(s) must be respected.

It is recommended to consider pre-existing medical co-morbidities, muscle size and activity, and experience from previous BoNT treatments of the subject (if applicable). No more than 20 U/kg BW NT 201 (max. total body dose of 500 U for subjects  $\geq 25$  kg BW) will be injected in this study. For safety reasons, the upper dose limit for subjects with GMFCS levels IV-V is restricted to 16 U/kg BW NT 201 (max. total body dose of 400 U for subjects  $\geq 25$  kg BW).

Doses for subjects of <25 kg BW are displayed in tables [Appendix 16.4](#). Above 25 kg BW fixed doses will be injected. The distribution of the total dose to clinical patterns per limb in this study is as follows:

[figure not shown]
[figure not shown]

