Laboratory data, unscheduled and doubly performed laboratory data will be listed individually. For additionally performed laboratory measurements of certain subjects on other visit dates or of other laboratory parameters than planned no descriptive statistics will be created.

If subjects have additional laboratory examinations during screening examination, only the last sample before application of study medication will be used for final analysis tables. No post-baseline laboratory data is planned for the MP.

Vital signs, body weight, height, and BMI

The individual blood pressure, heart rate, body weight, height, and BMI data will be listed and summarised (n, mean, standard deviation, minimum, 1st quartile, median, 3rd quartile and maximum) at each time point. Descriptive statistics will be given for absolute values and changes from baseline V2.

Frequencies of subjects with lowered, normal, or raised values will be displayed as shift tables from Baseline V2 vs. Control Visits V3, V4, and Final Visit V5.

High and low values are defined as given in Table 4.

Table 4: High and Low Values of Vital Signs

Vital Sign Variable	Flag	Observed Value
Systolic Blood Pressure (mmHg)	High	≥ 180
	Low	≤ 90
Diastolic Blood Pressure (mmHg)	High	≥ 105

Vital Sign Variable	Flag	Observed Value
Heart rate (bpm)	Low	≤ 55
	High	≥ 110
Height (cm)	High	Not applicable
	Low	Not applicable
Weight (kg)	High	Not applicable
	Low	Not applicable
BMI (kg/cm ²)	High	≥ 30
	Low	≤ 18.5

A value is considered as high/low if it meets the criterion for observed values

Botulinum Toxin Antibodies

For the subset of subjects with body weight greater or equal to 21 kg, frequency tables will be presented for Screening V1 by category (Fluorescence Immuno Assay for antibodies (FIA-AB)/Hemi diaphragm assay (HDA)), treatment group, pre-treatment status (treatment-naïve/pre-treated, i.e. pre-treatment with any BTX for any indication).

Investigator’s Global Assessment of Tolerability

Frequency tables and descriptive statistics will be generated for the data collected at Final Visit V5 of the Main Period.

The following analyses will be performed for the OLEX data:

C-SSRS

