For the sub-population of subjects enrolled after amendment 1.0 approval and of respective age and cognitive state the following analysis will be performed. Descriptive frequency tables will be displayed for total sub-population and by MP treatment group. The number of subjects who experience any suicidal ideation, suicidal behavior, or self-injurious behavior without suicidal intent at least once at any visit of the OLEX will be tabulated. Statistical evaluation of the data will be performed according to Table 1 of the Columbia–Suicide Severity Rating Scale Scoring and Data Analysis Guide Version 2.0 (Finalized February 2013) [Nilsson 2013 (5)]. Further C-SSRS data such as intensity of ideation and lethality data will only be listed.

Laboratory data

Descriptive statistics for absolute values at the Injection Visit V6 and the End of Study Visit (V17) and changes from Screening V1 to V6 and to V17 will be given for continuous variables.

The number of subjects with lowered, normal, or raised values compared to normal range as shift tables from Screening V1 vs. V6 and V1 vs. V17. Laboratory parameters will be sorted by predefined categories (e.g., hematology, differential count, and chemistry).

Laboratory data, unscheduled and doubly performed laboratory data will be listed individually. For additionally performed laboratory measurements of certain subjects on other visit dates or of other laboratory parameters than planned no descriptive statistics will be created. If subjects have additional laboratory examinations during screening examination, only the last sample before treatment start will be used. The first valid value for a post-baseline visit is analyzed.

Vital signs, body weight, height, and BMI

The individual blood pressure, heart rate, body weight, height, and BMI data will be listed and summarised (n, mean, standard deviation, minimum, 1st quartile, median, 3rd quartile and maximum) at each time point. Descriptive statistics will be given for absolute values and changes from baseline V2.

Frequencies of subjects with lowered, normal, or raised values will be displayed as shift tables from Baseline V2 vs. all available OLEX period visits.

Botulinum Toxin Antibodies

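### Growth retardation was seen in juvenile animals, but no age- and sex-standardised growth measure is planned, so raw height and weight changes have no usable reference in the open-label extension

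*SAP*

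**What the plan says.** **The animal finding.** Protocol 4.3 describes a juvenile rat study with reproductive findings at 30 LD50U/kg. Of lower doses it says "no indications of frank systemic toxicity other than growth retardation were seen at 10" LD50U/kg and below. It then leaves the meaning for patients open: "The clinical relevance of the findings from this animal study with these extremely high doses and reinjection already at" maximal paralysis is, it concludes, not known.

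**The population.** The inclusion criteria admit "Female or male subject 2 to 17 years of age (inclusive"). Treatment is one blinded cycle followed by up to three open-label cycles, 48 to 64 weeks in all.

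**The measurements.** Height, weight and BMI are taken at V1, V2, V5, V6, V10, V14 and V17 (Protocol 12.3.5.3). V5 values may be carried over to V6 when both visits fall on one day.

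**The analysis.** For both periods SAP 7.5.3 states "The individual blood pressure, heart rate, body weight, height, and BMI data will be listed and summarised" at each time point, and "Descriptive statistics will be given for absolute values and changes from baseline V2". SAP 7.5 gives safety tables by MP treatment group and in total. SAP 7.5.3 also plans to screen these variables for notable individual values or changes. SAP Table 4, which feeds the shift tables, enters height and weight as not applicable and gives BMI one fixed pair of limits for all ages. The age groups in SAP 7.7.5 apply to the Ashworth Scale and adverse events, not to height or weight.

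**The concern.** Healthy growth makes height and weight rise in nearly every child of this age over a year. A positive mean change is therefore expected whether growth is normal or slowed, and its size depends on the age mix of the subjects who contribute. To be informative, a raw change needs either a concurrent comparison group or an external age and sex reference.

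The plan has the first only in the MP, for one cycle, and has the second nowhere. Repeated exposure happens in OLEX, which has neither. The trial would then collect height and weight through V17 and report a table that cannot separate normal from slowed growth over the period when that question is most open.

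**Working it through.** **1. Figure to reproduce.** Neither document states a growth figure, so there is none. Height velocity (4 to 8 cm/year), the SD of 14-week height change (0.7 to 1.5 cm) and the population height SD (5 to 7 cm) below are assumptions.

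**2. What the MP comparison can show.** Inputs from SAP 3.1: 172 high-dose and 86 low-dose subjects, 14-week cycle. All are assumed to be measured at V5.

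- Expected gain at 6 cm/year: 6 x 14/52 = 1.62 cm.
- Difference detectable with 80% power, two-sided 5%: (1.96 + 0.84) x SD x sqrt(1/86 + 1/172) = 0.37 x SD.
- Power for 25% slowing, a difference of 0.25 x 1.62 = 0.40 cm: Phi(0.40 / (SD x 0.132) - 1.96).

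| SD of 14-week change (cm) | Detectable difference (cm) | As slowing at 6 cm/year | Power for 25% slowing |
|---|---|---|---|
| 0.7 | 0.26 | 16% | 99% |
| 1.0 | 0.37 | 23% | 86% |
| 1.5 | 0.56 | 34% | 53% |

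Over 4 to 8 cm/year the detectable slowing runs from 12% to 52%. The randomised comparison therefore carries information about large effects. It is limited to one cycle, the low arm is itself active so only relative slowing is visible, and no test is planned.

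**3. Whether the MP split helps in OLEX.** The low dose is 25% of the high dose, and every OLEX cycle uses the high-dose regimen. For subjects completing all four sessions at constant weight, cumulative dose in high-dose sessions is:

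- high arm: 1 + 3 = 4
- low arm: 0.25 + 3 = 3.25

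The low arm has had only 0.75/4 = 19% less by V17. The contrast between MP groups has largely gone.

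**4. What raw change shows in OLEX.** Mean change from V2 to V17 over 56 weeks = velocity x 56/52 x (1 - slowing). The z-score change is minus the lost height divided by the population SD.

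| Scenario at 6 cm/year | Raw change (cm) | z-score change (SD 7 to 5 cm) |
|---|---|---|
| Normal | +6.46 | 0 |
| 25% slowing | +4.85 | -0.23 to -0.32 |
| 50% slowing | +3.23 | -0.46 to -0.65 |

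Age mix alone can hide slowing. A child growing normally at 4 cm/year gains 4 x 56/52 = 4.31 cm. A child slowed by half from 8 cm/year gains 8 x 56/52 x 0.5 = 4.31 cm. The raw changes are identical. The z-score changes are 0 and about -0.62 to -0.86.

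**5. Individual level.** Listings and screening for notable changes are planned. With height and weight marked not applicable in Table 4 and no other rule stated, a reviewer has no criterion for what counts as notable. The BMI shift tables use fixed limits and do not measure linear growth.

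**The case against.** The strongest reply is that the plan does more than print a pooled mean. Changes are tabulated for randomised arms that differ fourfold in dose and should be balanced for age, every subject is listed, notable changes are screened, and a growth problem judged to be an adverse event would enter tables split by age, weight and GMFCS. This stands for the MP. A reader might infer that the planned tables cannot show slowed growth at all, or that raw change is the only analysis. The documents support neither.

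A reader might also set the rat dose beside the trial limit in "No more than 20 U/kg BW NT 201 (max. total body dose of 500 U" and infer an exposure overlap. The documents do not support that. The vial "contains an amount of sterile lyophilized solid material with biological activity of 100 mouse" LD50 units, and no rat-to-child conversion is given. The rats were reinjected at maximal paralysis, unlike these subjects. Above 25 kg doses are fixed, so units per kg fall as weight rises.

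Nor does the protocol name growth as its main juvenile-toxicity question. It is not a study objective, and height and weight are classed among the other safety variables.

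Finally, z-scores are an imperfect remedy. Children with cerebral palsy may drift from a general-population reference, so a fall in uncontrolled OLEX cannot by itself be put down to the drug. This limits interpretation, but a stratified z-score change still carries more information than a raw change with no reference.

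**Conclusion.** The point holds in this form: the protocol reports growth retardation in juvenile animals with unknown clinical relevance, yet no age- and sex-standardised growth measure is planned. In the MP, raw changes allow a short descriptive dose comparison that could reveal a large effect (25% slowing detectable with 53% to 99% power under the assumed SDs and 6 cm/year, were a test done). In OLEX they have no usable reference: 6.5 cm with normal growth against 4.8 cm with 25% slowing are both plausible means in a sample aged 2 to 17.

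The absence of a standardised measure rests on the text alone; the sizes rest on the assumed velocities and SDs. Efficacy conclusions and confirmatory testing are unaffected. It is a cheap improvement to a safety summary, worth making because this is the first pediatric programme for the product.

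**What to change.** In SAP 7.5.3:

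- Derive height-for-age and weight-for-age z-scores by sex and exact age, using one reference named before the MP is unblinded, at V2, V5/V6 (counted once when the measurement is transferred), V10, V14 and V17.
- Summarise change from V2 with 95% confidence intervals by MP treatment group and, for OLEX, overall and by the age groups (2-5, 6-11, 12-17) and GMFCS level groups already used elsewhere in the SAP.
- List subjects whose height z-score falls by a pre-set amount, for example 0.5. That value is a suggestion with no source in the documents; another is acceptable if fixed in advance.
- State that OLEX changes are descriptive, are read within child and within strata because of possible drift from a general-population reference, and cannot alone attribute slowing to the drug.

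The cost is SAP wording, one derived variable set, one summary table and one listing. Age, sex, height and weight are already collected, so no visit or procedure is added.

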7.5 Safety Variables

All safety analyses of the MP will be performed on the SES of the MP. All safety analyses of the OLEX Period will be performed on the SES of the OLEX period. Analyses will be based on both, total population and by Main Period treatment group (high, mid, low). For this purpose the Main Period treatment group as treated instead of as randomized will be used. In the unlikely case that a subject has received mid or low dose instead of the planned high dose during the OLEX Period, he/she will be analyzed in total group of the OLEX tables together with all other subjects with the correct high dose treatment.

For safety variables the last measurement before start of treatment is defined as baseline value.

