7.5.3 Other Safety Variables

Laboratory evaluations, vital signs, BMI, body weight, height, Investigator’s Global Assessment of Tolerability, and incidences of subjects with antibodies against BoNT-A will be analyzed descriptively (values and changes from baseline) and screened for individual notable values and/or changes. Results of the C-SSRS will be summarized descriptively.

The following analyses will be performed for the MP data:

C-SSRS

Additionally, to fulfill FDA requirements, prospective monitoring of suicidality with the C-SSRS should be considered the most important (but not the only) source of information concerning suicidality.

These C-SSRS assessments will be done in the subpopulation of subjects enrolled after amendment 1.0 approval only.

Suicidality will be assessed prospectively in subjects at baseline and all post-baseline visits. The appropriate version of this scale ensures the consistent application of this important measure regardless of indication or investigator experience with the subject matter. With C-SSRS in place, administration of this semi-structured clinician-based assessment scale is standardized. The C-SSRS quickly and efficiently identifies those subjects that require additional clinician follow up.

Following versions of the C-SSRS are to be applied only for subjects enrolled after amendment approval:

1. Children's baseline / screening version
2. Children's since last visit version.

The C-SSRS interview should only be assessed with children of respective age and cognitive state. Clear age cut-offs for the C-SSRS were not defined by the authors, but it has been found that administration is possible in general for children with a developmental age of about 7 years. Otherwise it should be documented in the eCRF that a child was not able to assess the C-SSRS at a respective visit.

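### SAP Table 4 applies one fixed set of BMI and high blood pressure limits to ages 2 to 17, so these descriptive shift tables say little about small children (minor)

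*SAP*

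**What the plan says.** SAP section 7.5.3 plans shift tables of lowered, normal and raised values for blood pressure, heart rate and BMI. In MP they are "displayed as shift tables from Baseline V2 vs. Control Visits V3, V4, and Final Visit V5". On the categories it says "High and low values are defined as given in Table 4", and the table footnote adds "A value is considered as high/low if it meets the criterion for observed values".

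The rows used here are:

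- systolic blood pressure: High at 180 mmHg or more, Low at 90 mmHg or less;
- diastolic blood pressure: High at 105 mmHg or more;
- BMI: High at 30 or more, Low at 18.5 or less, with the unit printed as kg/cm²;
- height and weight: not classified.

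Table 4 stands under the heading "The following analyses will be performed for the MP data". For OLEX the section says "Frequencies of subjects with lowered, normal, or raised values will be displayed as shift tables from Baseline V2 vs. all available OLEX period visits" and gives no limits. SAP section 3.2 gives the population as ages 2 to 17. SAP section 6.5.3 and Protocol sections 9.1.1.9 and 12.3.5.3 plan BMI or its components at V1, V2 and V5 in MP, not at V3 or V4.

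The heart rate row and any diastolic Low limit are left out, because the table is broken across a page there in the text available.

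**The concern.** The rule looks only at the observed value. Nothing in Table 4 separates a given BMI in a preschool child from the same BMI in an adolescent. The same holds for blood pressure. A single cut-off over ages 2 to 17 may therefore sort subjects by age and size rather than by abnormality.

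Two things follow. First, small children can enter the BMI table as Low at baseline for no reason other than size, and a subject who starts as Low cannot move lower. Second, the High pressure limits leave room for a large rise that the table still counts as normal.

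BMI is also the only body-size measure that the shift tables classify. Protocol section 4.3 reports growth retardation in a juvenile rat study and calls the clinical relevance of that study's findings unknown, so body size is a reasonable thing for the safety tables to follow. What is at stake is how informative one descriptive safety display is.

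**Working it through.** **Inputs.** The limits are those of SAP Table 4. BMI is read in kg/m²: a BMI of 16 kg/m² is 16/10,000 = 0.0016 kg/cm², so limits of 18.5 and 30 make sense only per m². The weights, heights and pressures below are illustrative assumptions, since the documents give no distribution of age, BMI or blood pressure. There is no figure in the plan to reproduce.

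**Who starts as Low on BMI.** BMI = weight / height². The height at which BMI equals 18.5 is 100 × √(kg / 18.5) cm:

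| Weight | Low from a height of about |
|---|---|
| 10 kg | 73.5 cm |
| 15 kg | 90.0 cm |
| 20 kg | 104.0 cm |
| 25 kg | 116.2 cm |

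**What happens to a child who starts as Low (height held constant).**

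- 25 kg at 125 cm: 25 / 1.25² = 16.0, Low. After a 10% weight loss 16.0 × 0.9 = 14.4, and after 20% 16.0 × 0.8 = 12.8; both Low, no shift. To leave Low the child must exceed 18.5 × 1.25² = 28.9 kg, a gain of 15.6%.
- 15 kg at 100 cm: 15 / 1.00² = 15.0, Low. After 10% loss 13.5, after 20% 12.0; no shift. To leave Low the child must exceed 18.5 kg, a gain of 23.3%.
- By contrast, a fall from 18.6 to 18.4 (1.1%) counts as a shift from normal to Low, while a fall from 16 to 10 (37.5%) does not count at all.

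**Which visits are affected.** Of the MP shift-table visits V3, V4 and V5, BMI is planned only at V5. The MP BMI table is therefore V2 against V5. In OLEX the BMI visits are V6, V10, V14 and V17, affected only if Table 4 applies there.

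**Systolic pressure.** 95 to 135 (+40), 100 to 160 (+60) and 91 to 179 (+88) all stay normal. From 100 mmHg a rise of 180 − 100 = 80 mmHg is needed to reach High. A rise from 89 to 95 does appear, as Low to normal.

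**Diastolic pressure.** 60 to 90 (+30) and 60 to 104 (+44) are not High. From 60 mmHg a rise of 105 − 60 = 45 mmHg is needed.

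**The case against.** The strongest reply is that the data are still reported. Individual blood pressure, weight, height and BMI are listed, and the section says "Descriptive statistics will be given for absolute values and changes from baseline V2". These variables are also "screened for individual notable values and/or changes". A fall from 25 to 20 kg would appear in the listing and in the change summaries for weight and BMI. Adverse events are collected under the broad definition in Protocol section 10.1, and SAP section 7.7.5 splits them by age and weight group. This stands and keeps the point small. It is not a complete answer: the notable-value screen states no criterion of its own, a group summary can dilute one child's change, and the subgroups in section 7.7.5 cover the Ashworth Scale and adverse events, not vital signs or BMI.

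A second reply concerns cause. Any table with three categories hides a further fall from the lowest one, whatever limits it uses. This also stands. The single limits decide how many children start as Low; they do not create the blind spot below it. For that reason age-specific limits alone would not be enough.

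A reader might go further and infer that the tables can show no rise in pressure, or that safety signals will be lost. The documents do not support either. A systolic rise across 90 mmHg changes category, and the other outputs remain.

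**Conclusion.** The point holds as a minor one. With single observed-value limits, Table 4 gives shift tables that carry little information on BMI in small children and on pressure rises short of the High limits. The arithmetic is exact for the illustrative children. How many subjects are affected cannot be estimated from the documents.

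The effect is confined to descriptive safety shift tables: BMI at V2 against V5 in MP, blood pressure at V3, V4 and V5, and the OLEX tables if Table 4 is meant for them, which the SAP does not say. A reader might infer that the comparison between dose groups is distorted. It is not: the same limits apply to all three MP groups, so sensitivity is reduced but no bias is introduced. No confirmatory test, type I error rate or power is touched.

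**What to change.** Amend the SAP before the MP database is closed and unblinded, the window that Protocol sections 8.4.2 and 12 allow for:

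1. Replace the BMI and blood pressure limits in Table 4 with age- and sex-appropriate reporting categories from a paediatric reference named in the SAP; for BMI, a BMI-for-age percentile or z-score.
2. Add a change-from-V2 category with cut-offs fixed in the SAP, because step 1 alone cannot show a further fall in a child already Low.
3. State which limits the OLEX shift tables use, and correct the BMI unit to kg/m².

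These are reporting categories, not rules for managing subjects. The cost is a look-up table by age and sex, one extra category and a label correction. No new data are needed; there is slightly more programming and output.
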